**AE reporting for CT.gov**

For the legal requirement of ClinicalTrials.gov, two required tables on TEAEs which are not serious adverse events with an incidence greater than 5% (5% was selected prior to database lock) and on serious TEAEs will be provided by system organ class and preferred term on the safety set population.

If for a same patient, several consecutive AEs (irrespective of study treatment causality, seriousness and severity) occurred with the same SOC and PT:

- a single occurrence will be counted if there is  $\leq$  1 day gap between the end date of the preceding AE and the start date of the consecutive AE
- more than one occurrence will be counted if there is  $>$  1 day gap between the end date of the preceding AE and the start date of the consecutive AE

The number of deaths resulting from SAEs irrespective of study treatment relationship will be provided by SOC and PT.

These summaries will be provided only after full study completion.

### **2.8.1.1 Adverse events of special interest / grouping of AEs**

In order to support the additional assessment of adverse events, adverse events of special interest and other safety topics will be summarized by treatment group, including the number (and proportion) of participants. In addition, the adverse events of special interest will also be summarized by seriousness and severity, and other safety topics will be summarized by seriousness. Adverse events of special interest and other safety topics used in this analysis are specified as follows. The search criteria including subcategoires will be defined in detail in an external file according to the latest version of eCRS at the DBL. This includes MedDRA version and Novartis MedDRA Query (NMQ) dictionary date. However, for major cardiovascular events (MACE), the outcome data (fatal/non-fatal) will also be used, the details is provided in [Appendix 5.2](#).

#### Adverse events of Special Interest

- Injection Site Reaction
- Hepatotoxicity\_Hepatic events
- New onset diabetes or worsening of diabetes mellitus

#### Other safety topics

- Renal events
- Hypersensitivity reactions
- Neurological events
- Neurocognitive disorders
- Ophthalmological events
- Major cardiovascular events (MACE)

The eCRS safety definitions used to identify AEs of special interest and other safety topics will be provided as a listing.

The number and percentage of participants who had injection site reactions (sign and symptom) will be summarized and listed.

Listing of participants with adverse event of special interest and other safety topics will be provided.

### **2.8.2 Deaths**

Overall deaths will be summarized and listed.

### **2.8.3 Laboratory data**

Laboratory values will be summarized by treatment group, including changes from baseline at each time point. Frequency table of results for categorical laboratory parameters will be presented by visit and time point.

Shift tables using the low, normal, or high classification (except for eGFR and HbA1c) will be used to compare baseline to the worst on-treatment value by treatment group. All data collected after first dose of double-blind treatment, from scheduled, unscheduled and premature discontinuation visits will be used.

The following ranges will be used for eGFR and HbA1c

- For eGFR, the categories will be Severe =  $<30$  mL/min/1.73m^2; Moderate =  $\geq 30$  to  $<60$  mL/min/1.73m^2; Mild =  $\geq 60$  to  $<90$  mL/min/1.73m^2; and Normal =  $\geq 90$  mL/min/1.73m^2.
- For HbA1c, the categories will be  $<5.7\%$ ,  $\geq 5.7\%$  to  $<6.5\%$ , and  $\geq 6.5\%$ .

The shift table dealing with the fasting glucose parameter will require the lab sample to be taken while fasting. Samples taken while the participant was not fasting will not be analyzed.

For selected laboratory tests, the number and percentage of patients meeting the clinically notable criteria at any time, considering all data collected after first dose of double-blind treatment, from scheduled, unscheduled and premature discontinuation visits, will be summarized by laboratory parameter and treatment group. Notable criteria are defined in [Appendix 5.3](#). Clinically notable criteria and notable liver criteria will be considered to be met when both of the following occur:

- Post-baseline values meet the thresholds listed in [Appendix 5.3](#)
- Baseline values or any prior post-baseline values do not meet the thresholds listed in [Appendix 5.3](#)

Furthermore, the number and percentage of participants meeting notable criteria in liver function test (LFT) will be summarized by treatment group considering on-treatment data from scheduled, unscheduled and premature discontinuation visits. LFT criteria are defined in [Appendix 5.3](#).

All laboratory data will be listed by treatment group, participant, and visit/time and if normal ranges are available abnormalities will be flagged.

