8.4.4.2 Other safety evaluations

Assessment of Cardiovascular Events

Information on CV events such as CV death, resuscitated cardiac arrest, non-fatal MI, and non-fatal stroke (ischemic and hemorrhagic) will be collected as AE data.

Injection site reactions

Injection site reactions (ISR) should be monitored at each visit from the Randomization (Day 1) visit onwards ([Table 8-1](#)) and through additional contacts with the participant between visits as needed. ISR including individual signs or symptoms at the injection site following study treatment administration should be recorded on an appropriate eCRF page. Every effort should be made to follow up with the participant until resolution of the ISR.

Anaphylactic reactions

Potential anaphylactic reactions should be assessed by Sampson criteria in [Section 16.5](#). If Sampson criteria are positive, confirmation by elevation of tryptase in blood plasma should be obtained within 30 minutes of the onset of anaphylaxis (or as soon as possible).

Hyperglycemia-related events

Laboratory results and newly added concomitant medications should be checked for potential hyperglycemia-related AEs.

Report 'New onset of diabetes' in participants with no medical history of diabetes when:

- HbA1C becomes $\geq 6.5\%$ and/or
- Two consecutive values of fasting plasma glucose that are ≥ 126 mg/dL
- If a new concomitant medication for control of plasma glucose is added, further information to assess for a diagnosis of new onset diabetes will be collected.

Report 'Worsening of the glycemic control' or 'diabetic complications' in participants with a medical history of disease (HbA1C $\geq 6.5\%$ at baseline) when:

- HbA1C increases from baseline $> 0.5\%$ and/or
- New concomitant medication or increase in dose of current antidiabetic therapy is initiated to improve the control of plasma glucose level

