**Table 5.3-1 Clinically notable laboratory abnormalities for selected tests**

Parameters	Criteria
Hematology	
Hemoglobin	≤ 10 g/dL
Hematocrit	≤ 0.8 × LLN
WBC (total)	≤ 2.8 ×10  / μL, ≥ 16 ×10  / μL
Platelet count	≤ 75 ×10  / μL, ≥ 700 ×10  / μL
HbA1c	≥ 6.5% and ≥0.5% change from baseline
Clinically chemistry	
Creatinine	> 2 mg/dL
CK	> 1 and ≤ 3 × ULN
CK	> 3 and ≤ 5 × ULN
CK	> 5 and ≤ 10 × ULN
CK	> 10 × ULN
ALT	> 1 and ≤ 3 × ULN
ALT	> 3 and ≤ 5 × ULN
ALT	> 5 and ≤ 10 × ULN
ALT	> 10 × ULN
AST	> 1 and ≤ 3 × ULN
AST	> 3 and ≤ 5 × ULN
AST	> 5 and ≤ 10 × ULN
AST	> 10 × ULN

Parameters	Criteria
Total bilirubin	$> 2 \times \text{ULN}$
ALP	$> 2 \times \text{ULN}$

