**Table 5.3-2 Notable liver function test values**

Criterion
ALT > 3 x the upper limit of normal range (ULN)
ALT > 5 x ULN
ALT > 8 x ULN
ALT > 10 x ULN
ALT > 20 x ULN
AST > 3 x ULN
AST > 5 x ULN
AST > 8 x ULN
AST > 10 x ULN
AST > 20 x ULN
ALT or AST > 3 x ULN
ALT or AST > 5 x ULN
ALT or AST > 8 x ULN
ALT or AST > 10 x ULN
ALT or AST > 20 x ULN
Total bilirubin > 1 x ULN
Total bilirubin > 1.5 x ULN
Total bilirubin > 2 x ULN
Total bilirubin > 3 x ULN
TBL >2xULN & DBL >ULN
TBL >2xULN & DBL >1.5xULN
TBL >2xULN & DBL >2xULN
ALP > 1.5 x ULN
ALP > 2 x ULN
ALP > 3 x ULN
ALP > 5 x ULN
ALT or AST > 3 x ULN and total bilirubin > 1.5 x ULN
ALT or AST > 3 x ULN and total bilirubin > 2 x ULN
ALT or AST > 5 x ULN and total bilirubin > 2 x ULN
ALT or AST > 8 x ULN and total bilirubin > 2 x ULN
ALT or AST > 10 x ULN and total bilirubin > 2 x ULN
ALT or AST > 20 x ULN and total bilirubin > 2 x ULN
ALP > 3 x ULN and total bilirubin > 2 x ULN
ALP > 5 x ULN and total bilirubin > 2 x ULN
ALT or AST > 3 x ULN and Total Bilirubin > 2 x ULN and ALP < 2 x ULN (Hy's law)

ALT = alanine aminotransferase, AST = aspartate aminotransferase, ALP = alkaline phosphatase,  
DBL = Direct bilirubin

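### SAP 2.8.3 counts a partial fall into a lower, still abnormal CK, ALT or AST band as a new notable value, because Table 5.3-1 uses closed bands

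*SAP*

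**What the plan says.** SAP 2.8.3 reports "the number and percentage of patients meeting the clinically notable criteria at any time", using everything collected after the first dose. It then defines when a criterion counts: "Clinically notable criteria and notable liver criteria will be considered to be met when both of the following occur". The first condition is "Post-baseline values meet the thresholds listed in" Appendix 5.3. The second is "Baseline values or any prior post-baseline values do not meet the thresholds listed in" the same appendix.

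SAP Table 5.3-1 has 20 rows. CK, ALT and AST take four rows each: >1 to ≤3, >3 to ≤5, >5 to ≤10 and >10 x ULN. Nine of these twelve rows are therefore bounded above. No text ranks the bands, restricts the count to the worst value, or excludes a participant who was already in a higher band.

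The HbA1c row reads "≥ 6.5% and ≥0.5% change from baseline".

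SAP Table 5.3-2 is built differently. Its single-analyte ALT and AST rows, and combined rows such as "ALT or AST > 3 x ULN", have no upper limit. CK does not appear in that table.

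**The concern.** A rule that asks whether a criterion is met now and was not met before identifies worsening only if a milder value cannot meet a criterion that a more severe value fails. Open-ended cut-offs have this property: anyone above 5 x ULN is also above 3 and above 1. Closed bands do not. A participant at 4 x ULN does not meet the >1 to ≤3 row, so a later value of 2 x ULN meets that row for the first time.

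The table is there to show, by arm, abnormalities that appear on treatment. As written, the lower bands mix values on the way up with values on the way down, and one rise and fall can put the same participant in several rows. For CK this is the only graded summary. Protocol 6.5.1 names confirmed CK elevation with symptoms or new renal dysfunction among its dosing criteria, so readers will look at it. Placebo and 100 mg have 54 participants each, so one extra hit moves a row by 1/54 = 1.9 percentage points; in the arms of 100 it moves it by 1.0.

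**Working it through.** The plan states no figure for this rule, so there is none to reproduce. The check applies the two conditions to the Table 5.3-1 bands.

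**Inputs.** The bands come from Table 5.3-1. Illustrative values, one per band and chosen for this check, are 0.8 (normal), 2, 4, 7 and 12 x ULN. The first value in each sequence is baseline.

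**Step 1: sequences, read row by row.** The word *or* in the second condition is ambiguous. It was read three ways: neither baseline nor any prior value in that row; baseline only; and a literal *or*. All three gave the same result in every sequence.

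| CK (x ULN) | Rows counted, closed bands | Rows counted, cumulative cut-offs |
|---|---|---|
| 4, 2 | >1 to ≤3 | none |
| 12, 7, 4, 2 | >5 to ≤10; >3 to ≤5; >1 to ≤3 | none |
| 0.8, 12, 4, 2 | >10; >3 to ≤5; >1 to ≤3 | >1, >3, >5, >10 |
| 2, 12 | >10 | >3, >5, >10 |
| 4, 0.9 | none | none |

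In the third sequence the >10 hit is a true worsening. The other two closed-band hits arise during recovery.

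**Step 2: all one-step moves that end in an abnormal band.**
- Falls to a lower abnormal band: 3 from the top band, 2 from the third and 1 from the second, so 6.
- Worsenings: 4 from normal, 3 from the lowest band, 2 from the second and 1 from the third, so 10.
- Closed bands, row by row: 6 of 6 falls and 10 of 10 worsenings counted.
- Cumulative cut-offs (>1, >3, >5, >10): 0 of 6 falls and 10 of 10 worsenings counted.
- Closed bands, with the second condition applied to the whole parameter (no row met before): 0 of 6 falls, but only the 4 worsenings that start from normal. A rise from 2 to 12 x ULN is missed.

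**Step 3: how many participants could fall from a high baseline.** A fall between abnormal bands needs a starting value above 3 x ULN. The documents give no CK distribution, so this range is an assumption. Take log-normal CK with median *m* of 0.6 to 0.8 x ULN, within-person log SD *w* of 0.45 to 0.6 and between-person log SD *b* of 0 to 0.5. Then P(baseline >3) = 1 − Φ( ln(3/*m*) / √(*w*² + *b*²) ).
- Low end: ln(3/0.6)/0.45 = 3.58, giving 0.02%, or 308 × 0.00017 = 0.05 participants.
- High end: ln(3/0.8)/√(0.36 + 0.25) = 1.69, giving 4.5%, or 308 × 0.0453 = 14 participants.

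This covers falls from baseline only. Extra rows from an on-study rise and fall come on top, in participants who did worsen.

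**Step 4: HbA1c.** Change at baseline is zero, so the baseline value can never meet this row and the second condition cannot exclude anyone on it. A fall from 8.0% to 7.0% meets the row if change is absolute (1.0 ≥ 0.5) and fails it if change is post minus baseline (−1.0 < 0.5). Rises from 6.3% to 6.9% and from 7.0% to 7.6% meet it either way.

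**The case against.** The strongest reply is that this is one descriptive table and that most of what it shows is reported correctly elsewhere.

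- **Liver.** Table 5.3-2 gives open-ended ALT and AST counts, and exclusion criterion 10 removes participants with unexplained ALT or AST above 3 x ULN confirmed on repeat. A reader might infer that the liver comparison is compromised. The documents do not support that; what remains for ALT and AST is mainly extra rows in Table 5.3-1 after an on-study rise and fall.
- **Glycaemia.** A reader might infer that improving HbA1c is counted as harm. That holds only if change is read as absolute; a signed reading already excludes falls. SAP 2.8.4 also reports worst and last on-treatment change, shifts with separate worsened and improved categories, and new-onset diabetes. Protocol 8.4.4.2 does state a direction in its own worsening rule ("HbA1C increases from baseline"), so the SAP row lacks a word rather than an analysis.
- **Recovery.** A reader might infer that any recovery is counted. It is not: a return to ≤1 x ULN gives no hit, and every counted value is still abnormal. In 0.8, 12, 4, 2 the participant has a genuine new abnormality; the fault is in the additional rows.
- **CK.** It also has changes from baseline at each time point, listings, and a low/normal/high shift table that "will be used to compare baseline to the worst on-treatment value by treatment group".
- **Reading.** The second condition says thresholds, in the plural, and the summary is by parameter, so a parameter-level reading is arguable.

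The first four points stand and limit the finding. The fifth does not rescue the rule: that reading removes the false hits only by missing 6 of 10 worsenings. Nor does any of the CK output grade the elevation, so the CK bands have no backup.

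**Conclusion.** The concern holds in limited form. On every row-by-row reading tried, SAP 2.8.3 combined with the closed bands of Table 5.3-1 counts a partial fall into a lower abnormal band as a new notable value. This follows from the text and needs no distributional assumption.

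It affects nine rows, in practice mainly those for CK. The primary and key secondary tests are untouched. The size is probably modest: under the assumed distributions in the working, between 0 and about 14 of 308 participants across all four arms could start high enough to fall between abnormal bands. That range illustrates scale and should not be quoted as a rate for this trial. A reader might also infer a bias towards or against inclisiran; nothing in the documents shows that these extra hits would differ by arm.

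The HbA1c wording is a clarification, not an established error.

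**What to change.** In SAP Table 5.3-1, replace the CK, ALT and AST bands with cumulative cut-offs (>1, >3, >5, >10 x ULN). Alternatively, keep the bands, classify each participant once by the worst post-baseline value, and count that band only if it is higher than the baseline band.

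In SAP 2.8.3, reword the second condition to say that neither the baseline value nor any prior post-baseline value meets the same criterion. Without one of the table changes, this wording alone does not solve the problem.

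In the HbA1c row, write an increase of ≥0.5 percentage points from baseline.

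The cost is a few sentences and a small programming change, with no new data. Protocol Table 16-2 also lists bands, but the change concerns only how the SAP counts and displays values, and the SAP already departs from that table by splitting ALT and AST above 5 x ULN. If Day 180 tables were produced under the present rule, record the change in SAP Section 4 so that the two sets of counts can be compared.

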## 2.8.4 Diabetes assessment

Diabetes will be assessed by the analysis of:

- TEAEs
- change in glucose-related laboratory values over time
- Shifts from baseline in glucose control category and,
- Incidence of post-baseline new onset of diabetes.

Note that diabetes related tables dealing with the fasting glucose parameter will require the lab sample to be taken while fasting. Samples taken while the participant was not fasting will not be analyzed.

### Diabetes TEAE

New onset/worsening of diabetes will be identified by the search criteria specified in [Appendix 5.2](#). The analysis will be performed for all participants and then by baseline diabetes status. A participant will be identified as being diabetic at baseline if the targeted medical history notes that the participant is diabetic or the baseline HbA1c value is  $\geq 6.5\%$ . This summary will be provided by treatment group.

### Change in Glucose-related Laboratory Values over Time

This analysis only utilizes laboratory data (fasting glucose and HbA1c). The change from baseline to the last on-treatment observation and the worst on-treatment observation will be summarized by treatment group, separately for fasting glucose and HbA1c for all participants and then by baseline glucose control status. Baseline glucose control status will be identified separately for fasting glucose and HbA1c using the values provided in the table below (note that medical history will not be taken into account for this analysis).

Parameter	Baseline Glucose Control Status	Baseline Laboratory Values
Fasting Glucose*	Normal	<100 mg/dL
	Impaired	$\geq 100$ to $<126$ mg/dL
	Diabetes	$\geq 126$ mg/dL
HbA1c**	Normal	<5.7%
	Impaired	$\geq 5.7$ to $<6.5\%$
	Diabetes	$\geq 6.5\%$

\*Average of Screening and Day 1 fasting glucose values will be considered as baseline. If one fasting glucose value is missing (Screening or Day 1), the assessment will be based on the available data.

\*\*Day 1 assessment will be considered as baseline. If missing, then the baseline will be based on assessment at screening visit.

### Shifts from Baseline in Glucose Control Category

Shifts from baseline in glucose control category will be summarized by treatment group in two different ways. The change from baseline to the worst-on-treatment and the last-on-treatment laboratory values (up to min (last visit, last dose +180 day)) will be used to classify the on-treatment glucose control category. Medical history will not be taken into account for this analysis.

Shift Category*	Baseline Category**	Post-baseline Category***
Normal to Normal (no change)	Fasting glucose <100 mg/dL AND HbA1c <5.7%	Fasting glucose <100 mg/dL on two consecutive occasions AND HbA1c <5.7%
Normal to Impaired	Fasting glucose <100 mg/dL AND HbA1c <5.7%	Fasting glucose $\geq$ 100 and <126 mg/dL on two consecutive occasions OR HbA1c $\geq$ 5.7 and <6.5%
Normal to Diabetes	Fasting glucose <100 mg/dL AND HbA1c <5.7%	Fasting glucose $\geq$ 126 mg/dL on two consecutive occasions OR HbA1c $\geq$ 6.5%
Impaired to Normal	Fasting glucose $\geq$ 100 and <126 mg/dL OR HbA1c $\geq$ 5.7 and <6.5%	Fasting glucose <100 mg/dL on two consecutive occasions AND HbA1c <5.7%
Impaired to Impaired (no change)	Fasting glucose $\geq$ 100 and <126 mg/dL OR HbA1c $\geq$ 5.7 and <6.5%	Fasting glucose $\geq$ 100 and <126 mg/dL on two consecutive occasions OR HbA1c $\geq$ 5.7 and <6.5%
Impaired to Diabetes	Fasting glucose $\geq$ 100 and <126 mg/dL OR HbA1c $\geq$ 5.7 and <6.5%	Fasting glucose $\geq$ 126 mg/dL on two consecutive occasions OR HbA1c $\geq$ 6.5%
Diabetes to Normal	Fasting glucose $\geq$ 126 mg/dL OR HbA1c $\geq$ 6.5%	Fasting glucose <100 mg/dL on two consecutive occasions AND HbA1c <5.7%

Diabetes to Impaired	Fasting glucose $\geq 126$ mg/dL OR HbA1c $\geq 6.5\%$	Fasting glucose $\geq 100$ and $<126$ mg/dL on two consecutive occasions OR HbA1c $\geq 5.7$ and $<6.5\%$
Diabetes to Diabetes (no change)	Fasting glucose $\geq 126$ mg/dL OR HbA1c $\geq 6.5\%$	Fasting glucose $\geq 126$ mg/dL two consecutive occasions OR HbA1c $\geq 6.5\%$

\*No change (Normal to Normal, Impaired to Impaired, and Diabetes to Diabetes), worsened (Normal to Impaired, Normal to Diabetes, and Impaired to Diabetes), and Improved (Impaired to Normal, Diabetes to Impaired, and Diabetes to Normal) categories will also be summarized.

\*\* Baseline of fasting glucose is defined as average of Screening and Day 1 assessment. If one fasting glucose value is missing (Screening or Day 1), the baseline will be based on the available data. For HbA1c, Day 1 assessment will be considered as baseline.

\*\*\*For post-baseline categories, if the post-baseline two consecutive fasting glucose measurements fall in separate categories, or if only one post-baseline fasting glucose measurement is available, then the post-baseline glucose control category will be defined based on the HbA1c measurement only. If HbA1c value is missing and two consecutive fasting glucose measurements fall in separate categories, the lower category will be used to determine the post-baseline category.

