^a Urinalysis will be evaluated by dipstick analyses at the investigational site locally (a standardized dipstick test will be supplied by the Central Laboratory). Urinalysis will be performed from a sample of mid-stream urine. In case of abnormal results, microscopy and other assessments will be performed at the central lab.

^b Blood samples for determination of coagulation parameters will be performed prior to start of study drug injection on Day 1.

^c HbA1c and eGFR are tested at screening, Day 90, 180 and 360 only.

^d eGFR will be calculated with the revised equations in Japan below ([Matsuo et al 2009](#)).

eGFR (mL/min/1.73m²) = 194 × Serum creatinine^{-1.094} × Age^{-0.287} × 0.739 (if female)

^e Blood samples for steroid hormones should be collected at the same morning time throughout the study due to diurnal variation.

^f Only for female before menopause. Blood samples for estradiol and progesterone will not be collected from the participants who are taking hormone replacement therapy and/or using oral, (estrogen and progesterone), injected or implanted hormonal methods of contraception or other forms of hormonal contraception.

^g Only for male

8.4.2 **Electrocardiogram (ECG)**

ECGs will be done with local ECG machines. ECGs must be recorded after 10 minutes rest in the supine position to ensure a stable baseline. The preferred sequence of cardiovascular data collection during study visits is ECG collection first, followed by vital signs, and blood sampling. The Fridericia QT correction formula (QTcF) should be used for clinical decisions.

Single 12 lead ECGs are collected. The original ECGs on non-heat-sensitive paper and a certified copy on non-heat sensitive paper, appropriately signed, must be collected and archived at the study site.

The ECG tracing must be labeled with study number, participant number, date and time, and filed in the study site source documents.

For any ECGs with participant safety concerns, two additional ECGs must be performed to confirm the safety finding. A monitoring or review process by the investigator should be in

place for clinically significant ECG findings throughout the study and especially at baseline before administration of study treatment.

Clinically significant abnormalities must be recorded on the eCRF as either medical history/current medical conditions or adverse events as appropriate.

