#### 2.1.1 General definitions

The screening period will be up to 14 days. The treatment period will be 360 days.

Study drug refers to the investigational drug inclisiran sodium and placebo.

Date of first administration of study drug, or first date of study drug, refers to the date when the first dose of assigned treatment is administered. Date of last administration of study drug/treatment, or last date of study drug, refers to the date when the last dose of assigned treatment is administered.

Study day is defined as: if after first date of study drug, then Study Day = Date – first date of study drug + 1; if before first date of study drug, then Study Day = Date – first date of study drug; Study Day 1 is defined as the first date of study drug; there is no Study Day 0.

The visits in all analyses are based on the eCRF data.

Baseline is defined as the last non-missing result prior to the initial treatment.

Both LDL-C and VLDL-C for the analysis will be based on the reflexive approach: the calculated LDL-C based on the Friedewald formula will be used; however, if the calculated LDL-C <40 mg/dL or Triglyceride >400 mg/dL, then the non-missing LDL-C using the Beta Quantification (BQ) method will be used instead. Safety data until last visit (EOS) will be summarized.

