### Incidence of Post-baseline New-Onset of Diabetes

The number of participants who shift from no diabetes at baseline to post-baseline new onset of diabetes will be summarized.

The participant with no diabetes at baseline are those who had no medical history of diabetes in the targeted medical history CRF, had HbA1c  $<6.5\%$ , and had fasting glucose  $<126$  mg/dL prior to the study treatment (the baseline fasting glucose is defined as the average of fasting glucose values at Screening and Day 1. If one of the baseline fasting glucose values is missing, the assessment will be based on the available data).

A 4-component analysis will be utilized to detect the post-baseline new onset of diabetes. The 4 components are provided below.

1. Diabetic TEAEs identified by the SMQ search (see [Appendix 5.2](#)), or
2. Post-baseline fasting glucose  $\geq 126$  mg/dL on two consecutive occasions, or
3. Initiation of anti-diabetic medication at any time post-baseline, or
4. At least one post-baseline HbA1c  $\geq 6.5\%$ .

The number of participants who have any of the 4 components will be summarized (post-baseline new-onset of diabetes) by treatment group.

This analysis will be performed separately for participants who had normal and impaired glucose control categories at baseline.

The time to new-onset diabetes will also be summarized by treatment group. The number and percentage of participants meeting the 4 week interval category (<4 weeks, 4 to <8 weeks, 8 to <12 weeks, 12 to <16 weeks,  $\geq 16$  weeks) will also be summarized. Only participants without diabetes at baseline will be included in the analysis. The time (weeks) to new-onset diabetes will be calculated from the date of the first administration of study drug.

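### The glucose-control shift table in SAP 2.8.4 takes baseline HbA1c from Day 1 with no fallback, but the protocol schedules no Day 1 HbA1c; read literally, the table's Normal baseline category is empty

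*SAP*

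**What the plan says.** SAP 2.8.4 plans a table of shifts between three glucose-control categories (Normal, Impaired, Diabetes) built from fasting glucose and HbA1c together. Baseline Normal is "Fasting glucose <100 mg/dL AND HbA1c <5.7" (per cent). Baseline Impaired and baseline Diabetes each join their glucose and HbA1c conditions with OR.

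The table's footnote sets the baseline values. Glucose is averaged over screening and Day 1, with a fallback: "If one fasting glucose value is missing (Screening or Day 1), the baseline will be based on the available data". For HbA1c the whole rule is "For HbA1c, Day 1 assessment will be considered as baseline".

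Protocol 8.4.1, Table 8-3 footnote c, gives the test days: "HbA1c and eGFR are tested at screening, Day 90, 180 and 360 only".

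Two other SAP rules bear on the same quantity. The footnote to the preceding table, on change in glucose-related values over time, reads "Day 1 assessment will be considered as baseline. If missing, then the baseline will be based on assessment at screening visit". Section 2.1.1 states generally: "Baseline is defined as the last non-missing result prior to the initial treatment".

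The new-onset diabetes analysis, later in 2.8.4, also refers to baseline category: "This analysis will be performed separately for participants who had normal and impaired glucose control categories at baseline".

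**The concern.** The shift-table footnote names a visit at which HbA1c is not scheduled. The only planned pre-dose HbA1c is the screening one, and the footnote does not allow it. Two adjacent tables in one section therefore carry different HbA1c baseline rules, and the stricter of the two cannot be met on schedule.

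At stake is the table meant to show whether glucose control worsens on treatment. If the footnote is programmed as written, the table cannot show anyone moving out of Normal. Some participants drop out of it altogether, and the new-onset split may lose one of its two strata. Two programmers could both follow the SAP and produce different tables.

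**Working it through.** There is no stated figure to reproduce. The check is one of dates and classification logic.

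**Step 1: dates.** HbA1c test days (Protocol Table 8-3, footnote c) are screening, 90, 180 and 360. The baseline day in the shift-table footnote is Day 1. There is no match; the only scheduled pre-dose value is at screening.

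**Step 2: classification.** Take three illustrative fasting glucose values (90, 110, 140 mg/dL), one in each glucose band, and three illustrative screening HbA1c values (5.4, 6.0, 7.0%), one in each HbA1c band. Apply the baseline definitions twice: once with HbA1c missing (the footnote read literally), once with the screening HbA1c. An OR condition is taken as met if its glucose part is met.

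| Glucose | Screening HbA1c | Day 1 only (HbA1c missing) | Screening value used |
|---|---|---|---|
| 90 | 5.4 | unclassified | Normal |
| 90 | 6.0 | unclassified | Impaired |
| 90 | 7.0 | unclassified | Diabetes |
| 110 | 5.4 | Impaired | Impaired |
| 110 | 6.0 | Impaired | Impaired |
| 110 | 7.0 | Impaired | Impaired and Diabetes |
| 140 | 5.4 | Diabetes | Diabetes |
| 140 | 6.0 | Diabetes | Impaired and Diabetes |
| 140 | 7.0 | Diabetes | Diabetes |

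Under the literal rule 0 of 9 profiles are Normal, and the 3 with glucose below 100 mg/dL have no category. With the screening value Normal is reachable and no profile is unclassified. Two profiles (110 with 7.0, and 140 with 6.0) then meet two categories at once, and the SAP states no precedence at baseline.

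**Step 3: effect on the table.** It has 3 × 3 = 9 shift rows, of which 3 start from Normal. The worsened total is the sum of Normal to Impaired, Normal to Diabetes and Impaired to Diabetes; 2 of these 3 start from Normal. Under the literal rule all of these rows are zero in every arm.

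**Step 4: effect on the new-onset split.** The SAP does not say whether the normal and impaired groups in that analysis are those of the shift table. If they are, the normal stratum is empty. The overall new-onset count is not touched: its entry condition is an HbA1c below 6.5% before treatment, which the screening value satisfies or fails without any Day 1 test.

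**The case against.** The strongest reply is that the SAP already supplies a usable baseline. The general definition in 2.1.1 yields the screening HbA1c, and the preceding table starts from the same Day 1 rule but adds the screening fallback, so the shift-table footnote looks like a shortened repeat of it. The documents elsewhere assume that a test done only at screening has a baseline: eGFR shares the HbA1c schedule, yet SAP 2.3.1 summarises baseline eGFR, and the notable-value criterion for HbA1c in SAP Table 5.3-1 uses change from baseline. A variable missing for everyone would also be noticed in programming.

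Much of this stands. The missing fallback is probably an oversight and the intended value is probably screening. It does not settle the matter, though. The same footnote already departs from the general definition for glucose, by averaging two visits, so it acts as a table-specific override, and nothing says that its HbA1c sentence is not one too.

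Three stronger inferences are tempting and are not supported:

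- A reader might infer that the trial cannot show worsening from normal at all. SAP 2.8.3 plans an HbA1c shift table with its own three categories and no Day 1 rule, and the change-over-time analysis reports by baseline status with the fallback. Both still show it.
- A reader might infer that the diabetes adverse event of special interest is compromised. That tabulation (SAP 2.8.1.1) rests on event search criteria and does not use this table.
- A reader might point to a participant with glucose 110 mg/dL and screening HbA1c 7.0%. The literal rule labels this person only Impaired, so a later HbA1c of 6.5% or more would count as worsening although it was present before dosing. That is true, but with the screening value the same person meets both Impaired and Diabetes. The case is therefore partly a separate problem of overlapping definitions, which correcting the baseline does not cure.

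**Conclusion.** The point holds as an inconsistency within the SAP and between the SAP and the protocol schedule. If the shift-table footnote governs, baseline HbA1c is missing for every participant on schedule, 3 of 9 rows and 2 of 3 worsened components are empty, and participants with glucose below 100 mg/dL cannot be placed. If the general definition governs, none of this happens; the SAP does not say which applies.

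The effect is confined to this combined table and, conditionally, to the normal/impaired split of the new-onset analysis. Both are descriptive, and no efficacy analysis is involved.

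The conclusion assumes that HbA1c was drawn as scheduled; an unscheduled Day 1 test is possible but not planned. It rests on footnote c of Protocol Table 8-3, since the visit grid of Table 8-1 could not be read in the available text. The footnote is explicit.

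**What to change.** Replace the HbA1c sentence in the shift-table footnote with: *For HbA1c, the last non-missing value before first dose (the screening assessment if no Day 1 value exists) is the baseline.* Apply the same rule to every analysis in 2.8.4, and say whether the normal/impaired split of the new-onset analysis uses the shift-table categories.

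In the same edit, state which category takes precedence when a participant meets both the Impaired and the Diabetes baseline definitions.

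The cost is a few lines of SAP text and no new data. The document history shows that the current SAP version postdates the primary analysis, so tables may already have been produced. Check which rule the program applied, and re-run the table if it used Day 1 only.
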